Participants randomized to the CPAP Group will then be scheduled for CPAP titration in the Sleep Laboratory of the VA Boston or VA Connecticut Healthcare System. All technicians in both Sleep Laboratories are Registered Polysomnography Technicians who are credentialed for human subjects research and have experience in the administration and titration of CPAP. CPAP titration will be performed overnight on a single night in the Sleep Laboratory. Participants will undergo polysomnography with a typical montage according to current American Academy of Sleep Medicine recommendations, including electroencephalogram, electro-oculogram, chin electromyogram, respiratory inductance plethysmography, finger pulse oximetry, leg electromyogram, and electrocardiogram. Airflow and mask pressure will be monitored and recorded from the CPAP device. Participants will be habituated to the preferred mask prior to study initiation. The CPAP device will be set to deliver pressure starting at 4 cm H₂O pressure. The CPAP pressure will be increased in increments of 1 cm H₂O, at intervals of no less than 10 minutes, in order to eliminate both obstructive and central apneas, with a maximum CPAP pressure of 20 cm H₂O.

The Research Coordinator will maintain contact with participants by telephone during

the first 7 days of CPAP treatment to assist with any troubleshooting. The CPAP device is capable of wireless transmission of utilization and efficacy data. At the end of the first week of CPAP use, and again at weeks 2, 4 and 8 (in advance of each scheduled interim telephone contact), the utilization data will be reviewed by the Research Coordinator who will judge their acceptability based on usage for at least 4 hours/night for at least 5 nights and absence of excessive mask leak. If adherence does not meet these targets, the Research Coordinator will discuss with the participant in an attempt to overcome barriers to adherence.

Healthy Lifestyle and Sleep Education plus Nocturnal Supplemental Oxygen (NSO Group)

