In addition to HLSE, this intervention includes nightly treatment with nocturnal supplemental oxygen (NSO). Oxygen therapy will be initiated at 2 lpm via nasal cannula, with routine clinical follow-up using overnight oximetry to assess adequacy of this flow rate. If needed, oxygen will be increased in 1 lpm increments as needed to (1) maintain baseline saturation >90%, and (2) to reduce the frequency of 3% oxyhemoglobin desaturation events to <5 per hour (independent of baseline saturation level). As oxygen at 2 lpm via nasal cannula has been shown to reduce the number of 4% desaturations during sleep in patients with sleep apnea by 89%, we anticipate that most participants will be adequately treated at 2-4 lpm. Oxygen is provided by a stationery oxygen concentrator. Adherence with oxygen use is measured by hours of machine use over the intervention period.

Interim telephone contact

Following initiation of therapy, study staff will make telephone contact with each participant at weeks 1, 2, 4 and 8 to identify any early problems with treatment adherence and to ascertain any adverse events. In particular, sleepiness will be re-assessed using the Epworth Sleepiness Scale and [name] or [name] will contact any patient whose Epworth Sleepiness Scale score is ≥ 16 or who provides a response of 2 or 3 on the item regarding drowsy driving. At week one the Healthy Lifestyle Education will be presented to each group over the phone in conjunction with education materials set home with patient at baseline visit.

Final study visit

After 12 weeks of intervention, participants will return for a final study visit at which time all procedures performed at the baseline visit will be repeated, including phlebotomy, echocardiography, cardiopulmonary exercise testing, and questionnaire administration. Participants will be asked to complete, while wearing the assigned therapy 24-hour ambulatory blood pressure monitoring.

Following completion of study procedures, each participant will be encouraged to accept referral to a sleep specialist within the VA to discuss treatment of sleep apnea.

Statistical analysis

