This study provides an opportunity to evaluate multiple intermediate measures that might shed light on the mechanism of benefit of CPAP or NSO. These analyses are considered exploratory in nature. As each of the secondary outcome measures is continuous, analysis of these variables will be treated in a similar fashion to the analysis of the primary study endpoints. For analysis of blood pressure, the 24-hour mean blood pressure and the ratio of mean nighttime to mean daytime blood pressure will also be analyzed.

Mean hours of use of therapy over the 3-month intervention period between CPAP and NSO groups will be compared using a one-factor analysis of variance, with appropriate modification as needed for deviation from normality. The number of adverse events and serious adverse events in each per study arm will be tabulated and categorized according to their severity, expectedness and relationship to the study intervention.

Sample size and power

Our primary goals are to establish the efficacies of CPAP and NSO compared to HLSE. Because past studies were suggestive of a more beneficial effect of CPAP or NSO compared to HLSE, we propose to randomize more subjects to the two experimental treatment groups. That is, we propose to allocate patients into CPAP, NSO or HLSE randomly according to a 2:2:1 ratio. This strategy also improves statistical power for the secondary comparisons between CPAP and NSO.

The sample size for this study was chosen to provide adequate power to detect a significant difference in LVEF between each treatment group and the control group (Aim

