associated with temporary pain at the time of needle insertion and may result in bruising at the needle insertion site. Rarely, fainting occurs with a blood draw. Portable sleep monitoring and ambulatory blood pressure monitoring may lead to minor sleep disturbance and some subjects may experience mild skin irritation from the sensors or electrodes used. Use of the blood pressure cuff may cause mild discomfort as the cuff is inflated. When the blood pressure cuff is worn for 24 hours, there may be some soreness in the arm. The administration of questionnaires may be stressful, although none ask sensitive information. The echocardiogram may cause transient discomfort as the ultrasound probe is pressed against the chest and upper abdomen. Cardiopulmonary exercise testing may cause shortness of breath, fatigue, muscle discomfort, and very rarely (<1:1,000) may be associated with heart attack or death. The intravenous (IV) catheter that will be placed for the exercise has a small chance of causing bruising or infection. Standard precautions will be followed in cleaning and sterilizing the area. If contrast is needed for the echocardiogram, there is a small chance of allergic reaction. There is a rare chance (1:10,000) that patients may be allergic to the microscopic bubble contrast (lipid shell and gas), thus allergies will be confirmed via patient medical charts and verbally with the patient prior to the injection of the contrast agent. Special efforts will be taken to reduce risks by watching each subject for 30 minutes after the echo contrast agent.

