identifiers. Only study personnel will have access to research data, which is kept either in locked cabinets, in password-protected computers in locked offices, or on secure password-protected drives located behind the VA firewall or at the Center for Clinical Investigation at Brigham & Women's Hospital. All personal data will be stored separately from de-identified research data, and will be stored in password-protected files behind the VA firewall or in locked cabinets within the VA. Blood and specimens will be stored using de-identified bar codes at the VA Boston and shipped to [name] laboratory, the VA Boston clinical lab for testing. Once the assays have been run on the samples, any leftovers will be destroyed.

Risks from cardiopulmonary exercise testing will be minimized by close physician supervision of testing, which will be performed by trained technicians in the Cardiopulmonary Exercise Laboratories at the VA Boston and VA Connecticut HCS sites, with emergency equipment readily available. Although patients will be encouraged to exercise to their symptomatic limits, if there are any signs of medical instability, the cardiologist will end the test before the symptomatic endpoint is achieved.

Phlebotomy will be performed by trained phlebotomists.

All CPAP devices will be equipped with heated humidifiers to minimize drying, and attention will be paid at set-up to identifying a best-fit mask to minimize mask discomfort and air leaks. Subjects will be contacted at weeks 1, 2, 4 and 8 to identify any early problems with treatment and to ascertain any adverse events, in particular the onset of dangerous levels of sleepiness. Participants will be extensively counseled at the baseline visit on safety measures related to excessive sleepiness. Participants randomized to NSO will be counseled on risks of fire from use of oxygen near open flames, including cigarettes.

Potential Benefits of the proposed Research to Human Subjects and Others

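### No adverse-event inquiry is scheduled after week 8 or during the CPAP arm's wait for titration, so event counts may be incomplete and may not cover the same window in each arm

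*Combined protocol and SAP*

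**What the plan says.** Two sections of the protocol place adverse-event ascertainment, and they agree.

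- **Interim telephone contact:** "Following initiation of therapy, study staff will make telephone contact with each participant at weeks 1, 2, 4 and 8". The stated purpose is "to identify any early problems with treatment adherence and to ascertain any adverse events".
- **Protection against risks:** "Subjects will be contacted at weeks 1, 2, 4 and 8 to identify any early problems with treatment and to ascertain any adverse events".

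The end of treatment is set under Final study visit: "After 12 weeks of intervention, participants will return for a final study visit". At that visit "all procedures performed at the baseline visit will be repeated, including phlebotomy, echocardiography, cardiopulmonary exercise testing, and questionnaire administration". No adverse-event question is listed.

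The start of CPAP is set in the CPAP Group part of the Treatment section: "Participants randomized to the CPAP Group will then be scheduled for CPAP titration in the Sleep Laboratory". No maximum wait is given. The same section ties the reviews of device data to the first week of CPAP use and to weeks 2, 4 and 8, each ahead of the scheduled call. The CPAP calls therefore run from the start of CPAP. HLSE slides and materials are handed over at the baseline visit. For oxygen, no step is listed between randomisation and start, although no start date is given either.

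The Statistical analysis section plans the safety table: "The number of adverse events and serious adverse events in each per study arm will be tabulated". Events are then grouped by severity, expectedness and relationship to the intervention. It states no collection window, person-time or participant-level count.

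**The concern.** A by-arm event table is easy to read only if every arm was asked the same question over the same period. As written, the last scheduled inquiry falls four weeks before treatment ends, and the clock starts at therapy rather than at randomisation. The first feature can thin out late events in every arm. The second can remove early post-randomisation events from one arm only.

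The protocol's own background gives reason to collect these data carefully. It reports a trend towards higher short-term mortality with CPAP in the multicentre Canadian trial and an acute fall in stroke volume and ejection fraction when CPAP is applied. It also reports excess mortality with adaptive servo-ventilation in a similar population. The Significance section presents this trial as groundwork for a long-term morbidity and mortality study. An incomplete safety table would be a weak input to that study.

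**Working it through.** The plan gives no figure for adverse-event coverage, so there is none to reproduce. The check uses the schedule, then an illustration.

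**Inputs from the protocol**
- Last scheduled call: week 8 (Interim telephone contact; Protection against risks).
- Treatment length: 12 weeks (Final study visit).
- Arm sizes: 39 CPAP, 39 NSO, 20 HLSE (Sample size and power).
- CPAP wait, w weeks: not stated. Assumed here to be 1, 2 or 4 weeks.

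**Step 1. Share of treatment with no scheduled inquiry, all arms**

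(12 − 8) / 12 = 4/12 = 33.3%. This treats each call as covering all the time since the previous one.

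**Step 2. Share of time from randomisation with no scheduled inquiry, CPAP arm**

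If the calls ask only about time on therapy, the share is (4 + w) / (12 + w).

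| Assumed wait | Uncovered | Covered, 8/(12 + w) |
|---|---|---|
| 1 week | 5/13 = 38.5% | 61.5% |
| 2 weeks | 6/14 = 42.9% | 57.1% |
| 4 weeks | 8/16 = 50.0% | 50.0% |

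The share stays at 33.3% for HLSE, and for NSO if oxygen starts without delay. If the first CPAP call asks back to randomisation, the wait is covered. The protocol sets no recall period, so either reading is possible.

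**Step 3. What the gap could hold (illustration)**

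Assume 1 event per person-year, range 0.5 to 2, with everyone followed to week 12.

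- Weeks 8 to 12, each active arm: 39 × 4/52 = 3.0 person-years, hence 3.0 events (1.5 to 6.0), out of 39 × 12/52 = 9.0 over 12 weeks (4.5 to 18.0).
- Weeks 8 to 12, HLSE: 20 × 4/52 = 1.54 person-years, hence 1.5 events (0.8 to 3.1), out of 20 × 12/52 = 4.6 (2.3 to 9.2).
- CPAP wait, at 1 event per person-year: 39 × 1/52 = 0.75 events for 1 week, up to 39 × 4/52 = 3.0 for 4 weeks.

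These are events that would occur without a scheduled inquiry. They are not events shown to be lost.

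**Step 4. Reading raw counts**

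At equal risk and follow-up, each active arm has 39/20 = 1.95 times as many events as HLSE. This is the allocation ratio and not a bias, but a table of counts alone leaves the reader to correct for it.

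**Step 5. After the change**

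With a week-12 question and a window from randomisation, scheduled coverage rises from 8/12 (66.7%) to 12/12 for HLSE and NSO. For CPAP it rises from 50.0–61.5% (assumed waits of 4 to 1 weeks) to 100%.

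**The case against.** The strongest reply is that the documents never say events are recorded only at the calls. Week 12 is an in-person visit. It includes a Health Questionnaire on medical history and a cardiologist's check of clinical stability before exercise, and the list of repeated procedures is not exhaustive. A hospital admission between weeks 8 and 12 would probably come up. The titration night is an attended overnight contact at the end of the CPAP wait. The section on stopping treatment expects serious events to reach the investigator without tying them to a call. The gap from week 8 to week 12 is also the same in every arm.

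Much of this stands, and it limits the claim to a risk. It does not remove the gap. None of these contacts is described as adverse-event collection, none sets a recall period, and the final visit cannot reach a participant who does not attend. The stopping rule governs treatment and sets no reporting route.

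Four stronger readings are tempting, and the documents do not support them.

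- **The final exercise test lies outside collection.** Human Subjects Potential Risks says the test "very rarely (<1:1,000) may be associated with heart attack or death". However, it is monitored and physician-supervised, so an acute event would be seen. Only delayed events are open to question.
- **CPAP's first week is over-collected.** The extra calls are for troubleshooting, every arm has a week-1 adverse-event call, and the oxygen arm has its own clinical follow-up with oximetry.
- **The CPAP wait is about 2 weeks.** Subtracting 12 weeks of therapy and about 1 week of screening from 3.5 months (about 15.2 weeks) leaves about 2 weeks. But the 3.5 months applies to all randomised participants, so the remainder says nothing about CPAP in particular.
- **The table is meant to show that the treatments are safe.** The remark on their general safety is background in the risk section. The plan tabulates events by arm and specifies no test.

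**Conclusion.** The concern holds as a gap in the written schedule. No adverse-event inquiry is scheduled for the last 4 of 12 treatment weeks (33%) or for the week-12 visit. The clock starts at therapy, so the CPAP wait precedes the first scheduled inquiry in that arm. Late events may be under-recorded in all arms, and CPAP counts may not cover the same window as HLSE and NSO. Neither under-recording nor a difference between arms has been shown, and the direction of any net bias is unknown.

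The 33% follows from the protocol alone. The CPAP figures rest on assumed waits of 1 to 4 weeks and on calls that ask only about time on therapy. The event numbers rest on an assumed 0.5 to 2 events per person-year and full follow-up. A reader might instead divide the protocol's national hospitalisations by national prevalence (1.1/5.7 million = 0.19 per patient-year). Those figures do not describe this trial's patients or its full range of adverse events, so they are not used here.

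The change is worth making because it is cheap. The primary efficacy analyses and the sample size do not depend on it.

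**What to change.** 1. **Interim telephone contact:** define one adverse-event window for all arms, from randomisation through completion of the final-visit procedures. State that the first call asks back to randomisation, so that a CPAP participant's wait for titration is covered.
2. **Final study visit:** add the same scripted adverse-event and hospitalisation question in every arm, covering the period since the week-8 call.
3. **Statistical analysis:** beside the event counts, report participants with at least one event over the number randomised in each arm (planned 39, 39 and 20), with person-time. Person-time also shows where follow-up ended early.

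The cost is a few sentences of protocol text, one question at an existing visit, and denominators in a table. The downside is slightly more coordinator time and a few more events to report.

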 - The patient may be screened for inclusion in the study and administered an HST at this time, but will not be eligible to complete a baseline visit until the 30 day window has passed
- Hospitalization for myocardial infarction or cardiac surgery within previous 30 days
 - The patient may be screened for inclusion in the study and administered an HST at this time, but will not be eligible to complete a baseline visit until the 30 day window has passed
- Presence of a left ventricular assist device
- History of heart transplantation
- Poorly controlled hypertension ($> 175/110$), **OR** severe renal failure requiring dialysis, **OR** prior stroke with functional impairment **OR** other severe, or uncontrolled medical problems that may impair ability to participate in study exams based on medical history and review of medical records.
- Severe chronic primary insomnia, with reported usual sleep duration < 4 hours
- Severe daytime sleepiness, defined as Epworth Sleepiness Scale score ≥ 18 or report of falling asleep driving during the previous year, unless determined by a study physician to be at low risk for motor vehicle accident
- Awake resting oxyhemoglobin saturation $< 89\%$
- Pregnancy
- Smoking by subject or other person in the subject's bedroom, or other open flame in bedroom

- Current use of a positive airway pressure device (including continuous or bi-level positive airway pressure or adaptive servo-ventilation) or supplemental oxygen therapy

Study Design

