device will be positioned in the participant's mouth during the exercise VO₂ peak, VO₂ at anaerobic threshold and VE/VCO₂ will be measured using a metabolic cart. During exercise, electrocardiogram waveforms and hemodynamics (maximum heart rate and blood pressure) will be monitored. Patients will exercise to their symptomatic limits, with encouragement to achieve a respiratory exchange ratio >1.0 (consistent with high physiological workload). However, if there are any signs of medical instability, the cardiologist will end the test before the symptomatic endpoint is achieved. In any instances of submaximal workload, analysis would focus on VO₂ at anaerobic threshold, VE/VCO₂ and other indices that do not depend on peak exercise performance.

Questionnaires

- Medical Outcomes Study SF36 Health-related Quality of Life Questionnaire. Each subject will complete the SF36 at their baseline and 3 month follow-up appointment. This questionnaire is a multi-purpose, short-form health survey that is widely used in research to estimate specific disease burden and to compare disease-specific benchmarks with general population norms. The questionnaire consists of 36 questions and provides an 8-scale profile of functional health and well-being scores (62).
- Kansas City Cardiomyopathy Questionnaire. Each subject will complete this questionnaire at their baseline and 3 month follow-up appointment. This questionnaire is widely used to evaluate quality of life in heart failure patients. It consists of 23 items which assess the level of impact of physical symptoms in this population such as shortness of breath, fatigue, peripheral edema, and difficulty sleeping. It also assesses the impact of psychological symptoms like anxiety and depression, as well as social functioning (63).
- CHAMPS Physical activity questionnaire for older adults (64). Each subject will complete this questionnaire at their baseline and 3 month follow-up appointment. This questionnaire is used to assess physical activity in our population.
- Health Questionnaire. Each subject will complete this questionnaire at their baseline and 3 month follow-up appointment. This questionnaire is used to collect data about medical history, and general but important health indicators, e.g., alcohol use, sleep quality, and restless leg symptoms.

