This study is a randomized clinical trial with three parallel treatment groups, designed to compare the active treatment groups (CPAP and NSO) to the optimal medical management comparator (HLSE). Baseline data will be summarized using standard descriptive statistics for demographic and baseline clinical characteristics by treatment group. Based on our experience with the HeartBEAT Study, the rate of dropouts during the course of the three-month trial is expected to be low and we do not expect dropouts

to be differential with respect to treatment group assignment. The main analysis will include all subjects completing the follow-up examination. For the purposes of a sensitivity analysis, a result of “no change” will be imputed for all drop-outs, and compared to the main analysis.

The analysis for each of the primary outcome measures (LVEF and peak VO₂) will consist of a one-factor analysis of variance comparing the mean changes from baseline in LVEF (or VO₂). As we postulate similar benefits from CPAP and NSO, we will specify two contrasts: CPAP vs. HLSE and NSO vs. HLSE as our primary analyses. In a secondary analysis, we will also compare the effects of CPAP to NSO for the purpose of hypothesis generation for subsequent larger studies. This analysis is a simple analysis of variance, with data transformation or adoption of rank-based inference if approximate normality is not present. While the randomization should achieve approximate balance on potentially confounding conditions, analysis of covariance models that employ adjustments for recruitment site, age, sex, sleep apnea severity, comorbid illness, smoking and alcohol use will be fit to potentially improve the efficiency of the treatment effect estimates. Should a significant difference between treatment and comparator be identified, further exploratory analyses will assess the relation of adherence to therapy to change in outcome measures.

In order to compare the effectiveness of the assigned interventions in controlling sleep apnea over the course of the study, an additional exploratory analysis will compare the change in AHI, change in time in periodic breathing, and change in time at SpO₂ <90% between the baseline and final portable sleep monitoring studies. This analysis will utilize a one-factor analysis of variance. Further exploratory analyses will assess the relation of effectiveness of control of sleep apnea to changes in the primary outcome measures.

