1). We have used effect estimates based on the meta-analyzed mean effect sizes for CPAP and NSO included in the AASM Practice Parameters paper (41) of 6.4%, and 5.0% for CPAP and NSO, respectively, and an estimated SD of change in LVEF of 4.8% based on previous reports of the effect of either ASV, CPAP or NSO (40, 42, 45-47) on LVEF in patients with sleep apnea. We use the Bonferroni method to account for 2 main comparisons and perform the test comparing each treatment to control at a 2.5% significance level. Using a two-sided two-sample t-test, an evaluable sample size of 34 in the NSO (or CPAP) group and 17 in the HLSE group will achieve 90% power to detect a difference of 5.0% with a significance level of 2.5% assuming a standard deviation of 4.8% in each group, and 98% power to detect a difference in LVEF of 6.4%; there will be 80% power to detect a difference as small as 4.4% between either active treatment group and the HLSE group.

Changes in peak V02 (Aim 2) will be compared in a similar fashion as changes in LVEF. An evaluable sample size of 34 in CPAP or NSO group and 17 in HLSE group will have 80% power to detect a difference of 0.92 standard deviations with a significance level of 2.5% using a two-sided two-sample t-test. Only one study of treatment of central sleep apnea in HF reports the SD of change in peak VO₂, which was 2.5 ml/kg/min (58). The reported change in peak VO₂ with treatment of central sleep apnea with NSO was 1.4-5 ml/kg/min, with a median of 2.5 ml/kg/min (47, 50, 55, 58). The power for this Aim therefore appears adequate.

For the exploratory comparison of CPAP and NSO, the sample sizes of 34 evaluable subjects per group will provide 80% power to detect a difference of 3.3% in change in LVEF, assuming a SD of change of 4.8% and a two-sided significance level of 5%.

As comparisons for secondary outcomes (Aim 4) are exploratory in nature, they will be performed at 5% significance level without multiple comparison adjustment. For comparisons in a continuous outcome between each treatment group and the control group, an evaluable sample size of 34 in CPAP or NSO group and 17 in HLSE group achieve 80% power to detect a difference of 0.84 standard deviations with a significance level of 5% using a two-sided two-sample t-test.

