The proposed sample size of 39 in each active treatment group and 20 in the HLSE group includes a 15% increase over the needed number of evaluable subjects, to allow for expected rates on non-completion of the protocol.

Reasons for stopping assigned treatment

As there is clinical equipoise with respect to the long-term benefits of treatment of sleep apnea in chronic HF, and the duration of the intervention is short at 3 months, there is no plan to discontinue assigned treatment due to therapeutic failure related to cardiac disease. However, as treatment of sleep apnea may be expected to improve sleepiness, any participant who develops unsafe levels of sleepiness that in the opinion of the PI place him or her at increased risk of motor vehicle accidents or other safety risks, will be treated for their sleep apnea off protocol. While serious adverse effects of either CPAP or supplemental oxygen are not anticipated, should any serious adverse events occur that in the opinion of the PI are treatment related, the treatment will be discontinued.

Human Subjects Potential Risks

The study procedures do not place the subjects at risk of harm or discomfort greater than those encountered in routine medical care. The vein puncture for blood drawing is

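### The completers-only main analysis is backed by one missing-data check, zero-change imputation, which nearly always repeats the completer test result, and the plan does not say how deaths before week 12 are counted.

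*Combined protocol and SAP*

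**What the plan says.** The Statistical analysis section sets the population for both primary outcomes: "The main analysis will include all subjects completing the follow-up examination". It expects that "the rate of dropouts during the course of the three-month trial is expected to be low", on the strength of an earlier study whose rate is not given, and it does not expect loss to differ by arm. The only missing-data sensitivity analysis is that a result of zero change "will be imputed for all drop-outs, and compared to the main analysis". The covariate-adjusted models in the same section are there for efficiency, not for missing data.

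Under Final study visit: "After 12 weeks of intervention, participants will return for a final study visit". No adherence condition is attached.

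Sample size and power rests on "an evaluable sample size of 34 in the NSO (or CPAP) group and 17 in the HLSE group"; the 39, 39 and 20 randomised figure "includes a 15% increase over the needed number of evaluable subjects".

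Drop-out is not defined, and no section says how a death before week 12 enters the LVEF or peak VO2 analysis. Adverse events are only tabulated. Reasons for stopping assigned treatment allows off-protocol treatment and discontinuation, without saying whether those patients stay in the analysis.

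**The concern.** A completer analysis is unbiased only if, within each arm, the patients lost resemble those who stay. In heart failure, loss can be linked to deterioration. Patients know their treatment and the arms differ in burden, so equal loss rates would not guarantee equal reasons for loss. If the active arm alone loses patients who were doing badly, the completer comparison favours treatment.

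A sensitivity analysis should reveal when a result depends on this. Giving every lost patient a zero does not do so for the test. It also never tries an outcome worse than no change, even for a patient who died. Agreement between the two planned analyses would look reassuring while carrying almost no information about this bias.

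**Working it through.** **Inputs.** From Sample size and power: SD of LVEF change 4.8 points; 34 vs 17 evaluable from 39 vs 20 randomised; two-sided 2.5% per comparison. From Background: annual mortality of 7.5% (usual-care arm of the ASV trial, LVEF below 45%, mainly central apnea) and about 20% (heart failure generally). The loss patterns below are assumptions.

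**The plan's own figures.** 34 × 1.15 = 39.1 and 17 × 1.15 = 19.6, matching 39 and 20. Planned loss is therefore 5/39 = 12.8% per active arm and 3/20 = 15.0% in HLSE. Power for 5.0 points is 89.7% by the normal approximation (stated: 90%) and 88.0% by the t-test.

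**Why zero imputation hardly moves the test.** Take SD 4.8 and an HLSE mean change of 0.

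- Completers: SE = 4.8 × √(1/34 + 1/17) = 1.426. With t(49) = 2.312 the significance threshold is 3.30 points.
- Zeros added: an observed difference D becomes D × 34/39. The pooled variance becomes [49 × 4.8² + D² × 34 × 5/39] / 57, and this is multiplied by (1/39 + 1/20).
- D = 3.30: the estimate falls to 2.88 and the SE to 1.249, so t = 2.30 against a critical t(57) of 2.30. Completers give t = 2.31 against 2.31. A borderline result stays borderline.
- D = 4.4: the estimate falls to 3.84 and the SE to 1.269. t goes from 3.09 to 3.02, both clearly significant.

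**Size of the bias.** If lost active patients average 1 SD (4.8 points) below active completers and HLSE loss is random, the bias is 4.8 × 5/39 = 0.62 point. Zero imputation leaves 0.62 × 34/39 = 0.54. With the same gap in both arms it is 4.8 × (5/39 − 3/20) = −0.1 point.

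**Simulation.** True effect 0, 200,000 trials, 5 and 3 lost, pooled t-test. Repeat runs differ by up to about 0.2 percentage points.

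| Assumed loss | Type I error, completers | Type I error, zeros |
|---|---|---|
| Random | 2.4% | 2.4% |
| Active arm only, gap 0.5 SD | 2.9% | 2.9% |
| Active arm only, gap 1 SD | 4.4% | 4.4% |
| Active arm only, gap 1.5 SD | 7.5% | 7.5% |
| Active arm only, worst five lost (gap 1.8 SD) | 10.7% | 10.6% |
| Both arms, gap 1 SD | 3.0% | 2.9% |

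In the 1 SD active-only case the mean SE falls from 1.37 to 1.18, and the two analyses agree in about 99.9% of trials. At a true effect of 4.4 they agree in 99.5%. There the point estimate does move, from 5.03 to 4.38.

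**What a delta analysis would show.** Let δ be how far lost active patients fall below what completers would predict. The result tips when D − (5/39)δ = 2.312 × SE(δ). Here SE(δ)² = 1.426² + [(34 × 5/39)δ²/57] × (1/39 + 1/20) = 2.033 + 0.00578δ². Solving:

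| Observed effect | Tipping δ (points) |
|---|---|
| 3.6 | 2.2 |
| 4.4 | 6.9 |
| 5.0 | 9.9 |
| 6.4 | 16.1 |

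The SE must be recomputed at each δ. Holding it at 1.426 would give (5.0 − 3.30)/(5/39) = 13.3 for an effect of 5.0, which overstates robustness.

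**Deaths by week 12**, constant hazard assumed: 98 × (1 − 0.925^(12/52)) = 1.7 and 98 × (1 − 0.80^(12/52)) = 4.9.

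**The case against.** The plan expects low, non-differential loss over three months. If that holds, the harm is small: the same 1 SD selection in both arms gives a bias of about −0.1 point, against treatment. The damaging pattern needs outcome-dependent loss in the active arm only, and the documents do not show it. Their nearest support is a trend to more short-term deaths on CPAP in the multicentre trial. No size is given, there was no difference in transplant-free survival, and it does not concern oxygen, which Background describes as well tolerated. A 0.5 SD gap costs little. The analysis set depends on completing the examination, not on adherence. All of this stands, and it limits the point to a sensitivity analysis that should be improved.

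Three stronger readings are tempting, and none is supported.

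- A reader might infer that the documents expect deaths by week 12. They state no such number; 1.7 to 4.9 is an extrapolation. The lower end comes from the population closest to this trial, and the rule that recently hospitalised patients "will not be eligible to complete a baseline visit until the 30 day window has passed" may lower it further.
- A reader might infer that the check fails only near a null effect, because zeros then resemble the completer mean. A false positive needs an observed difference of about 3.3 points, so the observed means are not near zero. The verdict survives because the SE shrinks too, and this still holds at a true effect of 4.4.
- A reader might infer that the check is worthless. It does move the point estimate usefully when the effect is real (5.03 to 4.38 at a true 4.4).

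**Conclusion.** The concern holds as a weakness of the sensitivity analysis and a gap in the handling of deaths. It is worth fixing, but it does not show that the primary analysis is invalid. Zero-change imputation cannot serve as a check on the significance test at the planned loss. The algebra shows this without any assumption about why patients leave. How much it matters does rest on an assumption: with selection in the active arm only, type I error runs from about 2.9% to 7.5% for gaps of 0.5 to 1.5 SD, with 10.7% as the extreme; with similar selection in both arms it is about 3.0%. The tipping values assume SD 4.8, loss of 5/39 and 3/20, and loss otherwise at random. They show that a result just above 3.30 points would be fragile, while one at 5.0 would tip only if lost active patients fell about 9.9 points short. The current plan cannot tell these two situations apart.

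**What to change.** Keep the completer analysis as primary, and zero-change imputation if wanted for the estimate. Before outcome data are seen, add to the Statistical analysis section:

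1. A multiple-imputation delta (tipping-point) analysis of all randomised patients in their assigned arms, with arm-specific deltas, the SE recomputed at each delta, and the tipping delta reported for the observed effect. The range is the analyst's choice, but for LVEF it should pass the tips for the planning effects (9.9 and 16.1 points). Do the same for peak VO2 in SD units. In the 1 SD active-only case, a delta of −4.8 brings type I error from about 4.2% to 2.4%.
2. A definition of drop-out and a statement that deaths before week 12 are not scored as zero change but enter a worst-rank sensitivity analysis. This supplements the delta analysis: if the five worst outcomes are lost and one of the five is a death, type I error falls only from 7.9% to 5.4% on the rank test.

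The cost is SAP wording and modest programming, with no extra patients. The downsides are wider intervals under the delta scenarios (in the 1 SD case the SE rises from 1.38 to 1.43 at −4.8 and 1.56 at −9.6) and a rank-scale result for the death analysis.

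Separately, Cardiopulmonary Exercise Testing says "In any instances of submaximal workload, analysis would focus on" indices other than peak VO2, while Statistical analysis makes change in peak VO2 a primary outcome for all completers. Those passages should be reconciled.
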